#### **Intra-operative Evaluation:**

The following intraoperative factors will be evaluated: operative time (calculated from the insertion of the resectoscope to the final removal of all resected prostatic tissues), blood transfusion requirement, and intraoperative complications such as bleeding, capsular perforation, and transurethral resection (TUR) syndrome.

#### **Post-operative Evaluation:**

Clot retention, hemoglobin reduction, and electrolyte imbalance will be detected and treated postoperatively.

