**-Methods of the study:**

**Pre-operative Evaluation:**

- History, which includes IPSS, the International Index of Erectile Function 5 items Questionnaire (IIEF-5Q), and the Male Sexual Health Questionnaire-Ejaculatory Dysfunction Short Form (MSHQ-EjD).

- Physical examination, which includes a digital rectal examination.

- A pre-operative lab study, which includes urine analysis, hemoglobin, creatinine, and PSA levels.

-Trans abdominal ultrasonography to determine prostate volume and post void residual (PVR) urine volume.

- Uro-flow-metry (Qmax).

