**Statistical analysis:**

Statistical analysis was done by SPSS v26 (IBM Inc., Chicago, IL, USA). Shapiro-Wilks test and histograms were used to evaluate the normality of the distribution of data. Quantitative parametric variables were presented as mean and standard deviation (SD) and compared between the two groups utilizing unpaired Student's T- test. Quantitative non-parametric data were presented as median and interquartile range (IQR) and were analyzed by Mann-Whitney test. Qualitative variables were presented as frequency and percentage and were analyzed utilizing the Chi-square test or Fisher's exact test when appropriate. A two tailed P value  $< 0.05$  was considered statistically significant

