**Table 5: Laboratory investigation of the studied groups**

[figure not shown]
		Group 1 (n=45)	Group 2 (n=45)	P value	Mean difference (95% CI)
Hemoglobin (g/dL)	Preoperative	13.34±1.85	13.88±1.35	0.121	-0.535(-1.21: 0.145)
	Postoperative	12.29±1.73	12.55±1.58	0.466	-0.256(-949: 0.438)
WBC (10^9/L)	Preoperative	8.23±3.27	8.1±2.88	0.842	0.13(-1.161: 1.42)
	Postoperative	10.18±2.09	10.55±3.22	0.524	-0.366(-1.50:0.772)
Creatinine (mg/dL)	Preoperative	1.18±0.41	1.07±0.36	0.195	0.106(-0.055: 0.267)
	Postoperative	1.11±0.24	1.1±0.33	0.874	0.009(-0.112: 0.132)
Total PSA (ng/mL)	Median	2.13	4.2	0.001*	1.41(0.60: 2.30)
	IQR	1.39 - 3.8	2.6 - 5.3		

\*Significantly different as P value  $\leq 0.05$ , WBC: White blood cell, CI: Confidence interval, PSA: Prostate-specific antigen

[figure not shown]
Hemoglobin, WBC and creatinine were insignificantly different at preoperative and postoperative between both groups.

Total PSA was significantly lower in group 1 than group 2 as (P value =0.001).

[figure not shown]

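### Hemoglobin reduction is named in the protocol but not reported; Table 5 tests levels only, and the direction of the hemoglobin contrast depends on how baseline is handled

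*Combined protocol and SAP*

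**What the plan says.** The Post-operative Evaluation section is a single sentence: "Clot retention, hemoglobin reduction, and electrolyte imbalance will be detected and treated postoperatively". A reduction is a change within a patient. The preoperative hemoglobin needed to compute it is in the protocol: "A pre-operative lab study, which includes urine analysis, hemoglobin, creatinine, and PSA levels". The Intra-operative Evaluation section separately lists "blood transfusion requirement, and intraoperative complications such as bleeding, capsular perforation, and transurethral resection (TUR) syndrome".

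The Statistical analysis section says that normally distributed quantitative variables were "compared between the two groups utilizing unpaired Student's T- test". It describes no change score, paired analysis or baseline adjustment. Significance is two-sided at 0.05.

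Table 5 (n=45 per arm) has one hemoglobin row for before surgery and one for after, each with its own between-arm test. The text below it concludes: "Hemoglobin, WBC and creatinine were insignificantly different at preoperative and postoperative between both groups". No table or results sentence gives a reduction. Figure 7 (hemoglobin) is not visible in the text available to us.

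**The concern.** The protocol names a change, and the results compare levels at two separate times. When the arms start at different levels, the two approaches can give different pictures, and here they do. Group 1 is lower after surgery, which on its own looks slightly unfavourable, yet its mean fall is smaller, which looks slightly favourable.

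Blood loss is a natural safety comparison between a limited and a complete resection. A reader can get the mean falls by subtracting rows of Table 5, but cannot get their SD, confidence interval or P value, because the pre/post correlation is not given. Only the holder of the patient-level data can supply these.

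**Working it through.** **Inputs (Table 5, mean ± SD in g/dL, 45 men per arm).** Preoperative: Group 1 13.34 ± 1.85, Group 2 13.88 ± 1.35, stated difference -0.535 (P=0.121). Postoperative: 12.29 ± 1.73 and 12.55 ± 1.58, stated difference -0.256 (P=0.466). The postoperative interval is printed, after its minus sign, as "0.256(-949: 0.438"; the lower limit is evidently -0.949.

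**Step 1: reproduce the stated figure.** Pooled SD = √[(1.73² + 1.58²)/2] = 1.657. SE = 1.657 × √(2/45) = 0.349. With the stated difference of -0.256 and 88 df, the 95% CI is -0.950 to 0.438 and P is about 0.466, as stated. (The rounded means give -0.26 and P=0.459.) The preoperative row also reproduces: SE 0.341, P about 0.121.

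**Step 2: mean reduction.** Group 1: 13.34 - 12.29 = 1.05. Group 2: 13.88 - 12.55 = 1.33. Difference, Group 1 minus Group 2: 1.05 - 1.33 = -0.28. The table's own differences give -0.535 + 0.256 = -0.279. A negative value here means that Group 1 fell less. This point estimate needs no assumption about correlation.

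**Step 3: precision of the reduction.** The SD of change in each arm is √(SDpre² + SDpost² - 2r × SDpre × SDpost), where r is the pre/post correlation, assumed equal in both arms. At r=0.5, Group 1: √(3.4225 + 2.9929 - 3.2005) = 1.79. Group 2: √(1.8225 + 2.4964 - 2.1330) = 1.48. SE of the difference = √[(3.2149 + 2.1859)/45] = 0.346.

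**Step 4: baseline-adjusted difference (ANCOVA approximated from the summary data).** Adjusted difference = -0.256 - b × (-0.535), where b is the pooled within-arm slope:

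b = r(1.85 × 1.73 + 1.35 × 1.58)/(1.85² + 1.35²) = 1.017r.

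With b=0 this is the level difference (-0.256). With b=1 it is the change-score result (+0.279). Positive values favour Group 1. At r=0.5, b=0.508 and the adjusted difference is -0.256 + 0.272 = +0.02. At r=0.7, b=0.712 and it is -0.256 + 0.381 = +0.13.

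| Assumed r | SD of change, Groups 1 and 2 | 95% CI for difference in reduction (estimate -0.28) | P | Adjusted difference (SE) | P |
|---|---|---|---|---|---|
| 0.3 | 2.12, 1.74 | -1.09 to 0.53 | 0.50 | -0.09 (0.340) | 0.79 |
| 0.5 | 1.79, 1.48 | -0.97 to 0.41 | 0.42 | +0.02 (0.309) | 0.96 |
| 0.7 | 1.39, 1.15 | -0.82 to 0.26 | 0.30 | +0.13 (0.256) | 0.63 |
| 0.8 | 1.14, 0.95 | -0.72 to 0.16 | 0.21 | +0.18 (0.216) | 0.41 |
| 0.9 | 0.81, 0.69 | -0.60 to 0.04 | 0.08 | +0.23 (0.159) | 0.15 |
| 0.95 | 0.58, 0.52 | -0.51 to -0.05 | 0.017 | +0.26 (0.117) | 0.029 |

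The adjusted estimate changes sign at r of about 0.47 (0.256/0.535 = 0.479; 0.479/1.017 = 0.47).

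**The case against.** The strongest reply is that the men were randomised, so level, change and baseline-adjusted level all estimate the same between-arm effect. They differ in precision and in how they treat a chance imbalance. That stands. A reader might infer from Step 2 that Table 5 has the wrong sign and that Group 1 really bled less; the documents do not support this. The change score subtracts the whole 0.535 g/dL baseline gap, although an arm that starts lower by chance is expected to fall less through regression to the mean. The adjusted estimate is close to zero at r=0.5 and less than half of 0.28 at r=0.7. At r=0.5 the interval for the change is no narrower than the published one.

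It is also fair to say that the protocol words the item as something to be found and treated, not as an endpoint, and that the stated aim is voiding, erectile function and ejaculation. Other bleeding-related results are given: transfusion 1 vs 2 (Tables 8 and 9) and clot retention 2 vs 4 (Table 9). Both are numerically lower in Group 1, so readers are not steered towards more bleeding there.

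Two further inferences go beyond the text:

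- **Postoperative transfusions were missed.** The tables put transfusion under intraoperative headings, but no section defines a time window. Whether later transfusions were counted is unknown.
- **No baseline electrolytes were taken.** The preoperative laboratory list is introduced as inclusive, and Table 5 reports a preoperative WBC that the list does not contain. Absence from the list therefore proves nothing.

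What remains is that a named quantity is unreported, that readers cannot construct its interval, and that the direction of the estimate depends on an analysis choice the Statistical analysis section does not make.

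**Conclusion.** The point holds as a reporting and analysis gap of modest size. On Table 5's figures, Group 1 is 0.256 g/dL lower by postoperative level and has a 0.28 g/dL smaller mean fall. An adjusted estimate would lie between the two, at about +0.02 at r=0.5 and +0.13 at r=0.7 (positive favouring Group 1). The level contrast has P=0.466 whatever r is. The reduction and adjusted contrasts stay above 0.05 for r up to about 0.9 and fall below it only at very high correlation (0.017 and 0.029 at r=0.95). Neither benefit nor harm is shown.

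The size and direction of the mean falls rest only on printed means. Every interval, P value and adjusted figure for the reduction rests on an assumed correlation, equal in both arms, and on all 45 men per arm having both values. The documents do not say whether the postoperative sample came before or after the three transfusions, so their effect on these means cannot be judged.

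**What to change.** Keep both hemoglobin rows in Table 5 and add:

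1. Each man's reduction (preoperative minus postoperative), as mean and SD by arm.
2. The between-arm difference with 95% CI from an ANCOVA adjusted for preoperative hemoglobin. Label it post hoc, because the Statistical analysis section does not provide for it.
3. A statement of when the postoperative sample was drawn, in general and relative to the three recorded transfusions, with a sensitivity analysis leaving those three men out.
4. A correction of the misprinted lower confidence limit in the postoperative row.

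For electrolyte imbalance, report the data if they exist. If they do not, say that no conclusion can be drawn.

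The cost is a small re-analysis of paired hemoglobin values already held and a check of three men's records. No new measurement is needed.

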#### **Follow up:**

All patients will be followed-up regularly at 3 and 6 months postoperatively with the IPSS, Qmax, PVR, IIEF-5Q, MSHQ-EjD Short Form, and rates of complications (including urethral stricture, incontinence, bladder neck contracture, Recatheterisation, UTI, and retrograde ejaculation).

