## Results

In this study, 103 patients were assessed for eligibility; 8 patients did not meet the criteria and 5 patients refused to participate in the study. The remaining patients were randomly allocated into two equal groups (45 patients in each). All allocated patients were followed-up and analyzed statistically (**Figure 42**).

[figure not shown]

[figure not shown]
Figure 1: CONSORT flow chart of the enrolled patients.

[figure not shown]

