**Table 9: Complications of the studied groups**

		Group 1 (n=45)	Group 2 (n=45)	P value
Intraoperative	Capsular perforation	1 (2.22%)	2 (4.44%)	0.620
	Intraperitoneal bladder perforation	0 (0%)	1 (2.22%)	
	Blood transfusion	1 (2.22%)	2 (4.44%)	
Early postoperative	Severe irritative LUTs	4 (8.89%)	7 (15.56%)	0.506
	Clot retention	2 (4.44%)	4 (8.89%)	
	Stress incontinence	1 (2.22%)	2 (4.44%)	
	Bladder neck contracture	1 (2.22%)	2 (4.44%)	
		Group 1 (n=43)	Group 2 (n=41)	P value
Late postoperative	Stricture bulbar urethra	1 (2.33%)	2 (4.88%)	0.699
	Bladder neck contracture	1 (2.33%)	2 (4.88%)	

LUTs: Lower urinary tract symptoms

Complications (intraoperative, early and late postoperative) were insignificantly different between both groups.

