**Figure 16: Complications of the studied groups.**

**Table 10: Post-operative preserved ejaculation, semen volume and concentration of the studied groups**

[figure not shown]
		Group 1 (n=43)	Group 2 (n=41)	P value	Median, mean difference or RR (95% CI)
Preserved ejaculation	After 3 months	35 (81.4%)	8 (19.51%)	<0.001*	18.05(6.07:53.64)
	After 6 months	34 (79.07%)	8 (19.51%)	<0.001*	15.58(5.37:45.25)
Semen volume (mL)	After 3 months	2.37±0.78	2.01±0.58	0.223	0.362(-229: 0.953)
	After 6 months	2.41±0.78	2.49±0.73	0.797	-0.079(-0.165: 0.535)
Sperm concentration (million sperm/mL)	After 3 months	35 (13.75-82)	72 (62.75-89.25)	0.036*	37(8: 60)
	After 6 months	32.5 (13-72)	86. (76-106.75)	0.005*	54(20: 78)

\*Significantly different as P value ≤0.05, CI: Confidence interval, RR: Relative risk

[figure not shown]
Preserved ejaculation (after three and six months) were significantly higher in group 1 than group 2 (P value <0.001).

Semen volume (after three and six months) was insignificantly different between both groups.

[figure not shown]
Sperm concentration (after three and six months) was significantly lower in group 1 than group 2 (P value<0.05).

**Figure 17:** Preserved ejaculation of the studied groups.

**Figure 18:** Semen volume of the studied groups.

[figure not shown]
**Figure 19:** Sperm concentration of the studied groups.

[figure not shown]

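### Table 9 finds no difference in complications but omits three that the protocol lists: UTI and recatheterisation appear nowhere, and retrograde ejaculation appears only indirectly, in Table 10

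*Combined protocol and SAP*

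**What the plan says.** The Follow up section sets assessments at 3 and 6 months, among them "rates of complications (including urethral stricture, incontinence, bladder neck contracture, Recatheterisation, UTI, and retrograde ejaculation". The list has six named items. The Statistical analysis section assigns qualitative variables to the "Chi-square test or Fisher's exact test when appropriate"; it defines no any-complication endpoint.

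Table 9 covers three phases:

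- **Intraoperative (45 and 45):** capsular perforation, intraperitoneal bladder perforation, blood transfusion.
- **Early postoperative (45 and 45):** severe irritative symptoms, clot retention, stress incontinence, bladder neck contracture.
- **Late postoperative (43 and 41):** bulbar urethral stricture, 1 v 2; bladder neck contracture, 1 v 2; P=0.699.

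The text below it reads: "Complications (intraoperative, early and late postoperative) were insignificantly different between both groups".

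Table 10 gives preserved ejaculation as 35/43 v 8/41 at 3 months and 34/43 v 8/41 at 6 months, and states: "Preserved ejaculation (after three and six months) were significantly higher in group 1 than group 2 (P value <0.001".

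**The concern.** Three of the six planned items (retrograde ejaculation, UTI, recatheterisation) have no row in Table 9, yet the sentence below it speaks of complications in every phase with no exclusion and no pointer to Table 10. A reader who takes complications to mean what the protocol lists will conclude that the two techniques do not differ on any of them. For retrograde ejaculation, the side effect that the experimental technique is meant to avoid, Table 10 points strongly the other way.

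For UTI and recatheterisation the reader cannot tell whether there were no events, whether the items were not collected, or whether they were left out. Clot retention is tabulated, but it is not a count of recatheterisations.

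**Working it through.** **Step 1. Planned list against reported rows.**

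| Planned item | Row in Table 9 | Elsewhere in the results |
|---|---|---|
| Urethral stricture | yes (late) | Table 12, by prostate size |
| Incontinence | yes (early, as stress incontinence) | Table 12, by prostate size |
| Bladder neck contracture | yes (early and late) | Table 12, by prostate size |
| Recatheterisation | no | none |
| UTI | no | none |
| Retrograde ejaculation | no | not under that name; Table 10 gives preserved ejaculation |

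**Step 2. Reproduce the printed late P.** Use a Pearson chi-square on three categories (stricture, contracture, neither) by two groups, with 2 degrees of freedom, so P = exp(−χ²/2). This layout treats the events as occurring in different patients.

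- With 45 and 45, the counts are 1 v 2, 1 v 2 and 43 v 41, with expected counts 1.5, 1.5 and 42 in each group. χ² = 4 × (0.5²/1.5) + 2 × (1²/42) = 0.667 + 0.048 = 0.714, and P = exp(−0.357) = 0.6997. This matches 0.699 if truncated.
- With the headed 43 and 41, the counts are 1 v 2, 1 v 2 and 41 v 37. χ² = 0.825 and P = exp(−0.412) = 0.662.

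The printed P therefore appears to use 45 per group, although the percentages in the same rows (2.33%, 4.88%) use 43 and 41. The Results text says "All allocated patients were followed-up and analyzed statistically", which also disagrees with 43 and 41. The four expected event counts are about 1.5, so an exact test suits these data. On 43 and 41, any late event v none gives Fisher P=0.427, and the exact test on the three categories gives 0.559. No version is significant.

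**Step 3. How much the late comparison can say.** If the events are in different patients, late events are 2/43 (4.7%) v 4/41 (9.8%).

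- Risk ratio = (2/43)/(4/41) = 0.48.
- SE of log RR = √(1/2 − 1/43 + 1/4 − 1/41) = 0.838.
- 95% CI = exp(ln 0.477 ± 1.96 × 0.838) = 0.09 to 2.46.

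**Step 4. Loss of ejaculation, from Table 10.** Not preserved is the complement of preserved.

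- 6 months: 43 − 34 = 9/43 (20.9%) v 41 − 8 = 33/41 (80.5%).
- χ² = 84 × (9×8 − 34×33)² / (43 × 41 × 42 × 42) = 29.8; P = 5×10⁻⁸.
- Risk ratio = (9/43)/(33/41) = 0.26. SE of log RR = √(1/9 − 1/43 + 1/33 − 1/41) = 0.306. 95% CI 0.14 to 0.47.
- 3 months: 8/43 (18.6%) v 33/41 (80.5%); risk ratio 0.23 (95% CI 0.12 to 0.44); Fisher P = 2×10⁻⁸.

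The 15.58 that Table 10 prints under the RR heading for 6 months is the odds ratio for preservation, (34×33)/(9×8), and should not be set against 0.26. The risk ratio for preservation is (34/43)/(8/41) = 4.05.

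**Step 5. Sensitivity of Step 4.**

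- *Not every loss is retrograde, same fraction in both groups.* At one quarter (about 2/43 v 8/41) Fisher P=0.046; at one fifth (about 2/43 v 7/41) P=0.085. The difference stays significant from about a quarter upward.
- *Different fractions.* If all 9 losses in Group 1 are retrograde, 18 of the 33 in Group 2 are enough for P<0.05 (9/43 v 18/41, Fisher P=0.035).
- *Missing patients.* Counting the 2 missing in Group 1 as losses and the 4 missing in Group 2 as preserved gives 11/45 v 33/45: risk ratio 0.33 (95% CI 0.19 to 0.57), Fisher P = 6×10⁻⁶.

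**The case against.** The strongest defence is that nothing about ejaculation is hidden. Table 10 follows directly, gives the counts by group at both visits with P<0.001, and states the result in words; Tables 11 to 13 examine it further. The Aim of the work names ejaculation as an efficacy outcome, so keeping it apart from surgical complications is reasonable. The sentence under Table 9 can be read as covering only the rows above it. All of this stands, and it limits the defect to the scope of one sentence plus two unreported items.

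A reader might infer three stronger things, none of which the documents support.

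- **That adding retrograde ejaculation reverses the result.** Group 1 already had fewer late events (2 v 4). Adding it would change significance, not direction.
- **That a protocol-defined composite is contradicted.** The protocol lists rates to record and defines no composite. Pooling would let 9 + 33 = 42 ejaculation losses swamp 6 stricture or contracture events and make the late comparison uninterpretable.
- **That components were dropped once the data were known.** Nothing in the documents shows when or why the rows were left out. For ejaculation the omission from Table 9 understates a benefit of the experimental technique, and the result is disclosed elsewhere.

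It is also fair to object that preserved ejaculation is not defined, so its complement could include men with no emission or no sexual activity. The 9/43 v 33/41 comparison is therefore conditional.

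The defence does not answer two points: UTI and recatheterisation appear in no table, and the Table 9 sentence carries no limit or cross-reference.

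**Conclusion.** The point holds as a mismatch between plan and report that should be corrected. Three of six listed complications are missing from Table 9, two of them from the whole document, and the conclusion is worded more broadly than the events tested.

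For the protocol's list the conclusion is not correct. Loss of preserved ejaculation at 6 months is about 60 percentage points lower in Group 1 (80.5 − 20.9 = 59.6). Reading this as retrograde ejaculation is an assumption, but the significance of the difference survives substantial departures from it and an adverse treatment of the six missing patients.

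For stricture and contracture the finding of no significant difference stands on either set of denominators. With six events and an interval from 0.09 to 2.46, though, it is not evidence that the groups are alike. Nothing can be said about UTI or recatheterisation.

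**What to change.** 1. Add separate rows for retrograde ejaculation, UTI and recatheterisation at 3 and 6 months on 43 and 41. Print 0 where none occurred, and say so if an item was not collected. State how retrograde ejaculation was determined and how it relates to preserved ejaculation in Table 10.
2. Do not pool retrograde ejaculation with stricture and contracture.
3. Recompute the late P on 43 and 41 with Fisher's exact test, which the Statistical analysis section already allows, and give risk ratios or risk differences with 95% CIs. Say whether any patient had more than one event.
4. Reword the conclusion along these lines: the listed surgical complications showed no significant difference, with wide confidence intervals, while loss of antegrade ejaculation was less frequent in Group 1 (see Table 10).

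The cost is a table and sentence edit. The ejaculation data are already reported, and the Follow up section required UTI and recatheterisation to be recorded. If they were not, one sentence saying so is enough.

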**List of abbreviations:**

BPH	Benign Prostatic Hyperplasia
LUTS	Lower urinary tract symptoms
BPO	Benign prostatic obstruction
TURP	Transurethral resection of the prostate
HRQL	health-related quality of life
RE	retrograde ejaculation (RE)
EjD	Ejaculatory dysfunction
QoL	Quality of life
IPSS	International Prostate Symptom Score
Qmax	Maximum urinary flow rate
PSA	prostate-specific antigen
UTI	urinary tract infection
IIEF-5Q	International Index of Erectile Function 5 items Questionnaire
MSHQ-EjD	Male Sexual Health Questionnaire-Ejaculatory Dysfunction
PVR	postvoid residual
TUR	Transurethral resection

**Statistical analysis:**

Statistical analysis was done by SPSS v26 (IBM Inc., Chicago, IL, USA). Shapiro-Wilks test and histograms were used to evaluate the normality of the distribution of data. Quantitative parametric variables were presented as mean and standard deviation (SD) and compared between the two groups utilizing unpaired Student's T- test. Quantitative non-parametric data were presented as median and interquartile range (IQR) and were analyzed by Mann-Whitney test. Qualitative variables were presented as frequency and percentage and were analyzed utilizing the Chi-square test or Fisher's exact test when appropriate. A two tailed P value  $< 0.05$  was considered statistically significant

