**Table 2: IPSS score of the studied groups**

	Group 1 (n=43)	Group 2 (n=41)	P value	Mean difference (95% CI)
Preoperative (0-35)	26.58±3.65	28.42±3.2	0.013*	-1.84(-3.28: -0.406)
3 months postoperative	7.14±2.99	6.68±2.43	0.446	0.456(-0.729: 1.642)
6 months postoperative	5.12±2.62	4.07±3.38	0.117	1.043(-0.265:2.352)

\*Significantly different as P value  $\leq 0.05$ , CI: Confidence interval, IPSS: International prostate symptom Score

IPSS score was significantly lower at preoperative (0-35) in group 1 than group 2 as (P value = 0.013) and was insignificantly different at (3 and 6 months) postoperative between both groups.

[figure not shown]

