**Figure 5: IIEF-5Q of the studied groups.**

**Table 4: MSHQ-EjD score of the studied groups**

	Group 1 (n=43)	Group 2 (n=41)	P value	Mean difference (95% CI)
Preoperative (1-15)	12.42±1.23	10.98±2.16	<0.001*	1.44(0.708: 2.181)
3 months postoperative	10.26±1.42	9.63±1.77	0.284	0.632(-0.544: 1.808)
6 months postoperative	10.62±1.76	10.38±2.26	0.741	0.243(-1.232: 1.717)

\*Significantly different as P value  $\leq 0.05$ , CI: Confidence interval, MSHQ-EjD: Male sexual health questionnaire – ejaculatory dysfunction short form, TTT: Treatment

MSHQ-EjD score was significantly higher at preoperative (1-15) in group 1 than group 2 (P value <0.001) and was insignificantly different at three and six months postoperative between both groups.

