**Table 7: PVR (ml) and Qmax (ml/sec) of the studied groups**

		Group 1 (n=43)	Group 2 (n=41)	P value	Mean difference (95% CI)
PVR (mL)	Preoperative	356 (250-380)	340 (289-391)	0.345	14(-20:48)
	3 months postoperative	55 (43.5-68.5)	39 (29-52)	0.003*	-13(-22: -4)
	6 months postoperative	49 (42.5-72)	34(22-47)	<0.001*	-21(-29: -12)
Qmax (mL/sec)	Preoperative	4.92±1.73	4.5±1.88	0.270	0.42(-0.334: 1.178)
	3 months postoperative	19.04±4.77	21.73±4.63	0.01*	-2.696(-4.738: -0.654)
	6 months postoperative	18.78±5.16	19.71±6.22	0.457	-0.93(-3.407: 1.55)

[figure not shown]
\*Significantly different as P value  $\leq 0.05$ , PVR: Postvoid residual, Qmax: Maximum urinary flow rate, CI: Confidence interval

PVR was insignificantly different at preoperative between both groups and was significantly higher at (3 months and 6 months) postoperative in group 1 than group 2 as (P value =0.003 and <0.001 respectively).

Qmax was significantly lower at 3 months postoperative in group 1 than group 2 as (P value =0.03) and was insignificantly different at (preoperative and 6 months postoperative) between both groups.

**Figure 12:** PVR of the studied groups.

**Figure 13:** Qmax of the studied groups.

[figure not shown]

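### Follow-up scores are compared without baseline adjustment although Group 1 began with milder IPSS, so worse symptoms in Group 1 may be understated, depending on an unreported correlation

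*Combined protocol and SAP*

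**What the plan says.** The Statistical analysis section compares groups one variable at a time. Normally distributed measures are "compared between the two groups utilizing unpaired" t-tests, skewed measures go to the Mann-Whitney test, and the threshold is two-sided 0.05. No ANCOVA, change-score or repeated-measures model appears anywhere.

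The baselines exist. The Pre-operative Evaluation list begins "History, which includes IPSS, the International Index of Erectile Function 5 items Questionnaire (IIEF-5Q" and goes on to MSHQ-EjD, residual volume and Qmax, which are the measures repeated at 3 and 6 months.

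Two of these baselines differ between the groups:
- **IPSS (Table 2):** Group 1 is 1.84 points lower, that is milder, P=0.013. The text then says follow-up IPSS "was insignificantly different at (3 and 6 months) postoperative between both groups". The printed differences are 0.456 at 3 months (P=0.446) and 1.043 at 6 months (P=0.117), with Group 1 worse at both visits.
- **MSHQ-EjD (Table 4):** "MSHQ-EjD score was significantly higher at preoperative (1-15) in group 1 than group 2", by 1.44 points, P<0.001.

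**The concern.** The stated aim covers voiding as well as ejaculation, so the IPSS sentence is one of the trial's main conclusions. Group 1 had the head start on symptoms yet is numerically worse at both visits. If men with worse baseline symptoms tend to have worse follow-up symptoms, the raw comparison credits the Group 1 operation with part of that head start. The adjusted difference against Group 1 would then be larger than the printed one, and the 6-month statement could change.

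The reason to adjust is that a measure's own baseline is usually prognostic for its follow-up. The baseline P value is not the reason, but the imbalance makes the omission matter here.

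**Working it through.** **Inputs.** From Table 2, mean ± SD for Groups 1 and 2: baseline 26.58±3.65 and 28.42±3.2; 3 months 7.14±2.99 and 6.68±2.43; 6 months 5.12±2.62 and 4.07±3.38. The header gives n=43 and 41. The within-group correlation r is an assumption, because no correlation and no SD of change is reported.

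**Reproducing the printed tests.** The pooled t-test at 43/41 with the printed differences gives:
- 3 months: P=0.447, CI -0.730 to 1.642 (printed 0.446, -0.729 to 1.642).
- 6 months: P=0.117, CI -0.266 to 2.352 (printed 0.117, -0.265 to 2.352).
- Baseline: CI -3.28 to -0.40 at 45/45 (printed -3.28 to -0.406), but -3.33 to -0.35 at 43/41. The printed gap therefore describes all 90 men, and the gap in the 84 analysed men is unknown.

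**ANCOVA from summaries.** Pooled SDs at 43/41 are 3.44 at baseline, 2.73 at 3 months and 3.01 at 6 months.

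Adjusted difference = printed difference - r × (SDpost/SDpre) × gap

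SE = SDpost × √[(1-r²) × 82/81] × √[1/43 + 1/41 + gap²/(82 × SDpre²)], on 81 df

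Example, 6 months, r=0.2, gap -1.84: 1.043 + 0.2 × (3.015/3.438) × 1.84 = 1.37. SE = 3.015 × √(0.96 × 82/81) × √(0.02326 + 0.02439 + 0.00349) = 0.672. Then t=2.03 and P=0.045.

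| r | 6 months (95% CI) | P | 3 months (95% CI) | P |
|---|---|---|---|---|
| -0.2 | 0.72 (-0.62 to 2.06) | 0.29 | 0.16 (-1.05 to 1.38) | 0.79 |
| 0 | 1.04 (-0.32 to 2.41) | 0.13 | 0.46 (-0.78 to 1.69) | 0.47 |
| 0.1 | 1.20 (-0.15 to 2.56) | 0.081 | 0.60 (-0.63 to 1.83) | 0.33 |
| 0.2 | 1.37 (0.03 to 2.70) | 0.045 | 0.75 (-0.46 to 1.96) | 0.22 |
| 0.3 | 1.53 (0.23 to 2.83) | 0.022 | 0.89 (-0.29 to 2.07) | 0.14 |
| 0.5 | 1.85 (0.67 to 3.03) | 0.003 | 1.19 (0.12 to 2.26) | 0.030 |

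Smallest r giving P<0.05, for different baseline gaps in the men analysed:

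| Gap | 6 months | 3 months |
|---|---|---|
| -1.84 (as printed) | 0.185 | 0.45 |
| -1.4 | 0.22 | 0.52 |
| -1.0 | 0.27 | 0.62 |

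**Other measures.** The same formula, with the printed baseline gaps of 0.42 for Qmax and -0.289 for IIEF-5Q and r from 0 to 0.5, leaves the 6-month conclusions unchanged. Qmax moves from -0.93 to -1.59 (P=0.46 to 0.15). IIEF-5Q moves from 2.27 to 2.44 (P about 0.001 or less). PVR is printed as medians and cannot be rebuilt this way.

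**MSHQ-EjD.** Table 4 is headed 43/41, but its follow-up tests do not reproduce at those numbers. They do reproduce at the counts with preserved ejaculation in Table 10 (35 and 8 at 3 months, 34 and 8 at 6 months). Using the printed differences:
- 3 months, 35/8: P=0.284, CI -0.544 to 1.808, as printed. At 43/41, P is about 0.075.
- 6 months, 34/8: P=0.741, CI -1.232 to 1.718 (printed 0.741, -1.232 to 1.717). At 43/41, P is about 0.59.

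**The case against.** The unadjusted comparison is a valid test: patients were "randomly allocated into two equal groups (45 patients in each", and a chance imbalance does not invalidate it. That stands. The point concerns bias given the imbalance that occurred, and precision.

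r is unknown and could be low. Entry required IPSS above 19, which narrows the baseline range, and follow-up means of about 4 to 7 lie near the bottom of the scale. With r at zero or below, adjustment does not raise the difference. The baseline gap in the analysed men is also unknown. All of this stands, and it is why the claim is conditional.

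The shift is small beside the improvement in both arms. At r=0.2 it is 0.32 points, against 6-month falls of 21.46 (26.58-5.12) and 24.35 (28.42-4.07). The printed interval already reaches 2.35, and no important IPSS difference is defined, so no change in clinical meaning is shown. That also stands. But with no equivalence margin set, the estimate and interval must carry the conclusion, and the adjusted ones take account of the unequal start.

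Other voiding results are not hidden. Table 7 shows higher residual volume in Group 1 at both visits and says "Qmax was significantly lower at 3 months postoperative in group 1 than group 2", with no significant Qmax difference at 6 months (P=0.457).

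Finally, an adjustment chosen after the results should not silently replace the original test. This is met by labelling it post hoc and printing both.

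**Conclusion.** The concern holds as a conditional one. The analysis ignores baselines that were collected, and in this sample any positive r means the raw IPSS difference favours Group 1. If the printed gap of -1.84 applies to the men analysed, the 6-month non-significance is lost once r exceeds about 0.185, and the 3-month one only above about 0.45. With a gap of -1.0 those values are 0.27 and 0.62.

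It cannot be said that the adjusted result is significant, because neither r nor the analysed men's baseline gap is reported. The calculation assumes a common within-group r and slope, and that the printed baseline SDs apply to the 43 and 41 men. The planned test is not invalid. What is insecure is resting the IPSS conclusion on its P value.

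For MSHQ-EjD the first problem is who was analysed. Table 10 reports "Preserved ejaculation (after three and six months) were significantly higher in group 1 than group 2". A comparison confined to men who kept ejaculation therefore selects on a post-surgery outcome that differs sharply by group, and baseline adjustment does not restore the randomised comparison.

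**What to change.** Add to the statistical analysis plan: *For IPSS, IIEF-5Q and Qmax, and for PVR on the log or rank scale, 3- and 6-month values are also compared by ANCOVA with randomised group and the baseline value of the same measure. The adjusted difference and 95% CI are reported beside the unadjusted test. This analysis was added after results were known and is post hoc.*

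Report the baseline means of the 43 and 41 men analysed and the observed r, and word the IPSS conclusion from the adjusted estimate and interval. Do not use change scores instead. They give 1.043 + 1.84 = 2.88 at 6 months whatever r is, which over-corrects when the regression slope is below 1.

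For MSHQ-EjD, first correct or state the analysed numbers. If only men with preserved ejaculation were scored, label the comparison as a post-surgery subset.

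The cost is a short re-analysis of data already held, in the same software. If r is near zero the 6-month IPSS interval widens slightly (width 2.73 against 2.62 as printed). The IPSS result may also become less favourable to Group 1.
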